3.6 Study sample size

Sample size calculation

The sample size estimation was conducted assuming an α level of 0.05, 90% power, an annual axial elongation of 0.40 mm with a standard deviation of 0.40 mm over 12 months (based on previous results from our study group), and a 50% treatment effect (reducing axial elongation by 0.20 mm). The required sample size was 86 participants per group, totaling 172 participants. After adjusting for a 10% loss to follow-up, the total sample size was 192 participants.

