7) Slit-lamp examination: Slit-lamp examination will be used to examine the anterior segment, lens, vitreous, and fundus, and any abnormalities will be recorded.

8) Optical coherence tomography (optional): SS-OCT fundus image acquisition and data processing: using swept source OCT (DRI OCT-1 Atlantis, Topcon) 9 Line Radial follow-up mode to scan and collect images to obtain fundus pictures and fundus tissue tomographic images. Before the collection, the subjects should be asked to sit still for a while, avoid taking coffee and drinks; during collection, doctors should pay attention to correct the axial magnification; researchers should concentrate on collection time to avoid the influence of the time rhythm fluctuation of choroidal thickness. After the choroidal boundary is automatically segmented by the machine's built-in software,

manual verification and correction are carried out, and the choroidal thickness data of 9 regions of the fovea and the inner, middle and outer rings (upper, lower, nasal, and temporal) are obtained.

2. Follow-up Examinations:

- 1) Questionnaire: A questionnaire on adverse events following the intervention will be administered at each follow-up visit and unexpected visits for children in the intervention group. Children and their parents/guardians will be asked about the side effects, including but not limited to short-term glare, flash blindness, and afterimages.
- 2) Visual acuity: An ETDRS chart (Guangzhou Xieyi Weishikang, Guangzhou, China) with standard illumination will be used to measure distance visual acuity. Visual acuity measurement is performed at a distance of 4 meters. Uncorrected visual acuity will be measured for each follow-up visit, best corrected visual acuity will be measured for the baseline, 6-month and 12-month follow-up visit.
- 3) Ocular biometric measurements via IOLMaster: IOLMaster will be used to measure the axial length of both eyes. Five measurements will be taken for each eye. The axial length measurement will be based on the mean of these five values if the desired precision (<0.05 mm) is achieved.
- 4) Cycloplegia: Cycloplegia will be induced with three drops of 1% cyclopentolate administered at the 0, 5th, and 20th minute to each eye. The light reflex and pupil dilation will be checked after an additional 15 minutes. Dilation and light reflex status will be recorded and full cycloplegia will be justified if the pupil dilates to 6 mm or greater and the light reflex is absent.

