5.2 Statistical analysis plan

The intention-to-treat (ITT) population comprised participants randomly assigned to either group. Data from all participants who attended at least one subsequent follow-up visit were included in the analysis, regardless of treatment or follow-up visit compliance. No imputation was used for the missing data. Individuals who switched to other myopia treatment modalities, such as orthokeratology or atropine eye drops, or discontinued the RLRL treatment, were censored. If a participant had only one eye with a SER exceeding -4.0 D, that eye was selected for the statistical analysis. In cases where both eyes were exceeding -4.0 D, the right eye was chosen for the analysis.

Treatment efficacy was assessed using longitudinal mixed models for primary (changes in AL) and secondary (changes in SER and IOP) outcomes at multiple follow-up visits. The mixed effects model was fitted with a random intercept and random slope for the participant, where the group, visit, group-by-visit interaction, baseline age, sex, and baseline AL were fixed effects. Estimated mean treatment differences and corresponding 95% confidence intervals (CIs) were derived from mixed models. UCVA alterations were classified into three categories: decline by two or more lines, stable (within a line), or improvement by two or more lines. The BCVA at the 12-month and baseline was evaluated against the 20/25 standard.

Sensitivity analyses were conducted to assess the treatment effects of therapy in controlling myopia progression, specifically axial elongation and SER progression, across different baseline SER and age groups.

A longitudinal mixed-model analysis was conducted to assess the relationship between treatment efficacy and compliance within the intervention group. Treatment compliance in the intervention group was measured as a percentage of the total number of assigned treatment sessions.

Safety analyses were performed in the ITT population. All adverse events were reported individually. Six ophthalmologists, one from each center, independently scrutinized the OCT scans for potential structural anomalies.

6.MONITORING

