Eyerising amblyopia comprehensive treatment instrument is mainly composed of treatment module, housing, eye mask, interpupillary distance adjustment knob, locking hand wheel, touch screen, control circuit, and electrical interface (as shown in Figure 1). The functions of each component structure are as follows:

- 1) Treatment module: an electronic module that realizes four treatment functions;
- 2) Shell: fix and install each component module, which is convenient for users to use the instrument;
- 3) Eye mask: The user's eyes are close to the eye mask during treatment, and the eye mask has a good wrapping property to prevent the interference of external light;
- 4) Interpupillary distance knob: The treatment device is a binocular product, and the user can adjust the distance of the emission window of the treatment device to be consistent with their own interpupillary distance, to achieve the best treatment effect;
- 5) Hand wheel lock: The user adjusts the pitch angle of the treatment head to the best position according to his height and posture, and then locks it with the hand wheel

lock to prevent loosening.

- 6) Touch screen: the user operates the machine through the touch screen;
- 7) Circuit control: control each electronic module;
- 8) Electrical interface: including power switch, power interface, USB interface and LAN interface.
- 9) Power switch: use for starting and closing the machine;
- 10) Power interface: connect the adapter for power supply;
- 11) USB interface: used for manufacturers to detect and debug internal circuits;
- 12) LAN interface: help machine connect to the external Internet.

Figure 1:

治疗眼罩: Treatment Eye Mask

激光辐射窗口: Laser Radiation Window

锁紧手轮: Hand Wheel Lock

触摸屏: Touch Screen

外壳: Shell

2. Specifications and models

RS-200-1A

3. Working principle and mechanism

The potential of low-intensity photochemical conversion can cause photochemical reactions in the retina, including increasing the activity of cytochrome C oxidase, changing gene expression to regulate the mitochondrial respiratory chain, and increasing the biological activity of nitric oxide. Also, it can increase Choroidal metabolism rate and circulation to improve scleral hypoxia, prevent or slow down the progression of myopia.

4. product indications and contraindications, precautions,

Indications:

- 1) It is suitable for patients with ametropia, anisometropia and strabismus amblyopia.
- 2) It is suitable for the treatment of juvenile myopia.

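### The one-eye rule is valid and meets the planned power, but it leaves the second qualifying eye unused; using it would tighten the 12-month axial length interval by about 1% to 8%

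*Combined protocol and SAP*

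**What the plan says.** Section 5.2 analyses one eye per child. If only one eye passes the -4.0 D threshold, that eye is used. Otherwise: "In cases where both eyes were exceeding -4.0 D, the right eye was chosen for the analysis". The mixed model has a random intercept and slope at child level and no eye level. The listed sensitivity analyses concern baseline SER and age groups, so no two-eye analysis appears even as support.

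On treatment and measurement:
- The device annex after the references states: "The treatment device is a binocular product". The instructions in 3.4 have the user fuse two light points.
- The follow-up part of 4.2 states: "IOLMaster will be used to measure the axial length of both eyes". The schedule in 4.3 places AL at screening and at all five follow-up visits, and spherical equivalent at screening, month 6 and month 12.
- The baseline AL item and both autorefraction items in 4.2 do not say which eyes are measured.

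Section 3.6 counts children, not eyes: "The required sample size was 86 participants per group, totaling 172 participants".

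**The concern.** In a child with two qualifying eyes, both eyes carry the same randomised allocation and both are followed. Unless the two eyes change in exactly the same way, the second eye adds information about that child's response. Setting it aside gives a wider interval for the AL difference than the same children could support. The same applies to SER if refraction is recorded in both eyes. What is at stake is precision only: the allocation, the unit of randomisation and the validity of the comparison are not in question.

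**Working it through.** **Inputs from 3.6.** The calculation is described as "assuming an α level of 0.05, 90% power", with "an annual axial elongation of 0.40 mm with a standard deviation of 0.40 mm over 12 months" and a 0.20 mm reduction as the effect. Sidedness is not stated; a one-sided test would need 69 per group, so only a two-sided test fits the plan's figure.

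**Inputs not in the documents (assumed).** ρ is the correlation between fellow eyes in 12-month AL change, taken as 0.7 to 0.95. p is the share of children with two qualifying eyes, taken as 70% to 100%.

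**Step 1: reproduce the plan.** The normal approximation gives n = 2 × (1.960 + 1.282)² × 0.40² / 0.20² = 84.1, so 85 per group. With the noncentral t, 85 per group falls just short (89.99%) and 86 gives 90.3%, which matches 86 per group. For dropout, 172 / 0.90 = 191.1, rounded up to 192, which matches "After adjusting for a 10% loss to follow-up, the total sample size was 192 participants".

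**Step 2: precision with one eye.** SE = 0.40 × √(2/86) = 0.0610 mm. The 95% half-width is 1.96 × 0.0610 = 0.120 mm.

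**Step 3: effect of the second eye.** The mean of two equally variable eyes has variance (1 + ρ)/2 relative to one eye. With children weighted equally, the variance factor is V = p(1 + ρ)/2 + (1 − p). Interval width scales with √V, and power is recomputed with the noncentral t at SD 0.40 × √V and 86 per group.

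| p | ρ | V | Change in CI width | Half-width (mm) | Power |
|---|---|---|---|---|---|
| one eye only | – | 1.000 | – | 0.120 | 90.3% |
| 0.7 | 0.95 | 0.983 | −0.9% | 0.119 | 90.8% |
| 1.0 | 0.95 | 0.975 | −1.3% | 0.118 | 91.0% |
| 0.7 | 0.9 | 0.965 | −1.8% | 0.117 | 91.3% |
| 0.8 | 0.8 | 0.920 | −4.1% | 0.115 | 92.5% |
| 1.0 | 0.7 | 0.850 | −7.8% | 0.110 | 94.3% |

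**Step 4: does the nested model differ from the child mean?** A mixed model with eye nested in child weights a two-eye child by 2/(1 + ρ) relative to a one-eye child: 1.18 at ρ = 0.7 and 1.03 at ρ = 0.95. Its variance factor is 1 / [2p/(1 + ρ) + (1 − p)]. At p = 0.7 and ρ = 0.7 that is 0.890, against 0.895 for equal weighting. The table serves for either.

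**Step 5: the nesting is essential.** If all children had two eyes and these were entered as independent, the SE would be understated by the factor 1/√(1 + ρ), about 0.73 at ρ = 0.9.

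These figures treat the 12-month result as a two-group comparison of means, as 3.6 does. They leave out covariate adjustment and the earlier visits.

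**The case against.** The strongest reply is that nothing here is broken. The one-eye rule is fixed in advance, does not depend on outcome, covers both the one-eye and two-eye case, and agrees with a sample size counted in children. All of that stands, so this is a choice between two valid analyses.

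The reply also limits the size of the gain, and this stands too. A reader might take the most favourable corner (ρ = 0.7, every child with two qualifying eyes), which is worth 1/0.85 − 1, or about 18% more children, as the expected gain. The documents give neither figure, and at ρ = 0.95 the interval narrows by only about 1%. Nor should much be expected from averaging out measurement error. Section 4.2 already averages three readings at baseline and five at follow-up, with a 0.05 mm tolerance, against an SD of 0.40 mm. The gain has to come from real differences in growth between fellow eyes.

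A reader might also infer that both eyes are stated to be measured at every visit and for refraction. The text says so only for follow-up AL. At baseline it is implied, because AL change needs a starting value and the anisometropia criterion compares the eyes, but the sponsor should confirm it.

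Finally, a two-eye analysis is not just extra rows. Admitting all eyes that meet the full entry criteria would bring in the astigmatism and BCVA limits, and could drop a right eye that the present rule includes. The eye-level slope, the baseline covariate and the weighting of children also have to be specified. These objections shape the fix; they do not remove the gain.

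**Conclusion.** A low-cost improvement, not a correction. A reader might conclude that the one-eye rule biases the comparison or leaves the trial underpowered. The documents do not support either: the rule is valid, and the planned 90% power is met with one eye per child. What holds is that data from a treated and followed second eye go unused. Under the assumed ranges for ρ and p, using them takes the 95% half-width from 0.120 mm to between 0.119 and 0.110 mm, and power at 86 per group from 90.3% to between 90.8% and 94.3%. Strong correlation between fellow eyes would put the result near the low end. Against a target effect of 0.20 mm, much of this range would not alter the trial's conclusion. The direction is certain for any correlation below 1; the size is not.

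**What to change.** Amend 5.2 before unblinded data are seen:
- Keep the -4.0 D threshold as the only eye-selection rule, and word it to match the entry criterion. Entry admits an eye at exactly -4.0 D, whereas the analysis rule asks for more than that and leaves such an eye without a clear place.
- Include every eye that meets the threshold in the AL and SER models, with a random intercept and slope for the child, a random intercept for eye within child (plus a slope if the model converges), and eye-specific baseline AL.
- State that the child remains the unit of randomisation, and keep the right-eye analysis as a sensitivity analysis.
- For the baseline-SER group analyses, say whether grouping is by eye or by child, since anisometropia up to 3.0 D can put one child's eyes in different groups.
- Confirm in 4.2 that baseline AL and all refraction are recorded in both eyes.

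A simpler equivalent is to analyse each child's mean over qualifying eyes. It needs no extra variance level and keeps children nearly equally weighted.

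The cost is SAP wording, one more variance level to estimate and somewhat more weight for children with two qualifying eyes. If both eyes are already recorded throughout, no measurement is added. If unblinded data have already been seen, keep the one-eye analysis as primary and add the two-eye model as a labelled supportive analysis.

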8.2 Plan modification

8.3 Informed consent

8.4 Confidentiality

1. ABSTRACT

Basic information on clinical practice of medical devices:

Device Classification: Class II medical devices

Specification Model: RS-200-1A

Date: September 20, 2020

Sponsor: Zuoguan Medical Devices Co., Ltd. at Suzhou Industrial Park

Practice Title

A Randomized, Controlled, Multi-centre Clinical Study on the Effectiveness and Safety of repeated low-level red-light (RLRL) for myopia control in children and adolescents with high myopia

Practice Purpose

A Study on assessing the effectiveness and safety of RLRL for myopia control in children and adolescents with high myopia.

Subject Population

Subject: Children aged 6-16 with at least one eye with myopia of cycloplegic spherical equivalent refraction (SER) at least -4.0 D

Sample size: 192 subjects are planned to be enrolled and assigned to the intervention group or control group according to a ratio of 1:1

Practice Design

Overall design:

This prospective, single-blind, parallel-group, multi-center randomized clinical trial was conducted at six tertiary hospitals. Participants between 6 and 16 years old with at least one eye with a spherical equivalent refraction (SER) of -4.0 D or greater were recruited. The enrolled participants were randomly placed at a 1:1 ratio into

intervention (RLRL treatment plus single-vision spectacles) or control (single-vision spectacles) groups. The participants attended follow-up appointments 1, 3, 6, 9, and 12 months after the baseline evaluation.

Outcomes:

1. Primary Outcome: Change of Axial length (AL, mm) at 12-month follow-up
2. Secondary Outcome: Change of cycloplegic spherical equivalent (SE, D) at 12-month follow-up
3. Optional Indicators:

Changes of uncorrected visual acuity (UCVA), best-corrected visual acuity (BCVA), intraocular pressure, etc.;

Changes of corneal thickness (CT), anterior chamber depth (ACD) and lens thickness (LT);

Observe macula and the structure of fundus around the optic disc;

Observe the choroid/retinal thickness of the fundus;

Compliance index: frequency of equipment uses.

Safety assessment

- ① Sudden vision loss;
- ② Afterimage time over 5 minutes;
- ③ Side effects such as glare, photophobia and flickering;
- ④ Structural damage to retina: tissue disruption or discontinuity, edema, or other abnormalities in the photosensory layer of the SS-OCT images;
- ⑤ Increased intraocular pressure etc.

Participants selection and exclusion criteria:

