Treatment efficacy was assessed using longitudinal mixed models for primary (changes in AL) and secondary (changes in SER and IOP) outcomes at multiple follow-up visits. Sensitivity analyses were conducted to assess the treatment effects of therapy in controlling myopia progression, specifically axial elongation and SER progression, across different baseline SER and age groups.

A longitudinal mixed-model analysis was conducted to assess the relationship between treatment efficacy and compliance within the intervention group.

Safety analyses were performed in the ITT population. All adverse events were reported individually.

Ethics:

The practice protocol (including the informed consent form) is submitted to the ethics committee for approval, and all subjects entering the trial screening must sign the informed consent form. Researchers should conduct experiments in strict accordance with the experimental protocol and GCP requirements to fully protect the legal rights and safety of the subjects.

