3.5 Outcomes

1. Primary Outcome: Change of Axial length (AL, mm) at 12-month follow-up
2. Secondary Outcome: Change of cycloplegic spherical equivalent (SE, D) at 12-month follow-up
3. Optional Indicators:

Changes of uncorrected visual acuity (UCVA), best-corrected visual acuity (BCVA), intraocular pressure, etc.;

Changes of corneal thickness (CT), anterior chamber depth (ACD) and lens thickness (LT);

Observe macula and the structure of fundus around the optic disc;

Observe the choroid/retinal thickness of the fundus;

Compliance index: frequency of equipment uses.

[figure not shown]

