- 5) Cycloplegic auto-refraction: Cycloplegic auto-refraction will be conducted using an auto-refractor (KR-8800, Topcon, Tokyo, Japan). The same auto-refractor will be used throughout the study. It will be calibrated before each examination session to ensure there is no equipment drift during the long follow-up process.
- 6) Slit-lamp examination: Slit-lamp examination will be used to examine the anterior segment, lens, vitreous, and fundus, and any abnormalities will be recorded.

7) Optical coherence tomography (optional): Swept Source-OCT (DRI OCT-1 Atlantis, Topcon) will be used to capture the macular scan. Shooting mode: 12 mm radial scan mode (follow up mode).

8) Safety assessment

- ① The incidence of allergic reactions;
- ② Afterimage duration exceeds 5 minutes;
- ③ Decreased near visual acuity;
- ④ Levels of side effects such as photophobia and blurred vision;
- ⑤ Increased intraocular pressure, headache, nausea and vomiting, etc.

Follow-up Schedule

(1) Visit 1: Screening period (-7~0 days)

- 1) Sign the "Informed Consent";
- 2) Record the general information of the patient;
- 3) Record the medical history;
- 4) Perform visual inspection, axial inspection, intraocular pressure inspection, equivalent spherical lens measurement, slit lamp inspection, OCT inspection;
- 5) Review the inclusion and exclusion criteria;
- 6) Record the combined/concomitant medication;

(2) Visit 2: Enrolment and randomization (day 0)

- 1) Randomly group, and the intervention group will receive experimental devices;
- 2) Record device defects;
- 3) Record the combined/concomitant medication;

(3) Visit 3: Day 30±14

- 1) Perform visual inspection, axial inspection, and intraocular pressure inspection;
- 2) Record the combined/concomitant medication;
- 3) Record adverse events/device defects.

(4) Visit 4: Day 90±14

- 1) Perform visual inspection, axial inspection, and intraocular pressure inspection;

2) Record the combined/concomitant medication;

3) Record adverse events/device defects.

(5) Visit 5: Day 180±14

1) Perform vision examination, axial examination, intraocular pressure examination, equivalent spherical lens, slit lamp examination, and OCT;

2) Record the combined/concomitant medication;

3) Record adverse events/device defects.

(6) Visit 6: Day 270±14

1) Perform visual inspection, axial inspection, and intraocular pressure inspection;

2) Record the combined/concomitant medication;

3) Record adverse events/device defects.

(7) Visit 7: Day 365±14

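### IOP is an optional indicator and a safety item in the outcome and safety lists but a secondary outcome under treatment efficacy in the SAP; its only specified analysis is a one-eye mean difference, with no definition or by-arm count of IOP rises

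*Combined protocol and SAP*

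**What the plan says.** Section 3.5 names a single secondary outcome: "Secondary Outcome: Change of cycloplegic spherical equivalent (SE, D) at 12-month follow-up". IOP comes below it, under the optional indicators: "Changes of uncorrected visual acuity (UCVA), best-corrected visual acuity (BCVA), intraocular pressure, etc". The abstract's outcome list has the same ordering.

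Raised IOP is also a safety item in two places, without a threshold in either. The abstract's safety assessment ends with "Increased intraocular pressure etc", and the follow-up safety assessment in 4.2 has "Increased intraocular pressure, headache, nausea and vomiting, etc".

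The analysis text assigns IOP differently. The abstract's summary reads "Treatment efficacy was assessed using longitudinal mixed models for primary (changes in AL) and secondary (changes in SER and IOP) outcomes at multiple follow-up visits", and section 5.2 repeats it, again listing "secondary (changes in SER and IOP) outcomes at multiple follow-up visits". The output specified there is a mean: "Estimated mean treatment differences and corresponding 95% confidence intervals (CIs) were derived from mixed models". Section 5.2 puts one eye per child into the analysis, the right eye when both qualify. The same paragraph gives visual acuity a per-child classification ("UCVA alterations were classified into three categories: decline by two or more lines, stable (within a line), or improvement by two or more lines") but gives IOP none.

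The safety paragraph of 5.2 says that safety is analysed in the ITT population, that adverse events are reported individually, and that ophthalmologists review the OCT scans. The schedule in 4.3 has IOP measured at screening and at all five follow-up visits in both arms.

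**The concern.** Two things are at stake.

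The first is outcome status. A reader following 3.5 expects one secondary outcome; a reader following 5.2 expects two. The abstract disagrees with itself, so it cannot settle the matter.

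The second is fit to purpose. The plan describes no IOP benefit from the device, and a history of glaucoma or ocular hypertension is an exclusion. The reason the documents give for watching IOP is the safety lists, and the question there is whether some children's pressure rises. A mean difference between arms answers a different question. It is also confined to one eye per child, although the device description calls the product binocular, so a rise in the fellow eye lies outside the model.

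**Working it through.** **1. The texts side by side**

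| Place | Status of IOP | Secondary outcome(s) |
|---|---|---|
| Abstract, outcome list | Optional indicator | SE at 12 months only |
| Section 3.5 | Optional indicator | SE at 12 months only |
| Abstract, safety assessment | Safety item, no threshold | not applicable |
| Section 4.2, safety assessment | Safety item, no threshold | not applicable |
| Abstract, analysis summary | Secondary, under treatment efficacy | SER and IOP |
| Section 5.2 | Secondary, under treatment efficacy | SER and IOP |

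The rows cannot all be followed. None of them comes from an amendment log.

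**2. The plan's own figure**

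The only design calculation is for axial length (section 3.6: difference 0.20 mm, SD 0.40 mm, 90% power, α 0.05, taken as two-sided). The normal approximation gives n = 2 × (1.960 + 1.282)² × 0.40² / 0.20² ≈ 84.1, so 85 per arm. The t-based solution is 85.03, so 86. Then 172 / 0.90 = 191.1, so 192. The stated figures reproduce. The IOP point does not depend on them; it only borrows 86 evaluable per arm.

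**3. How sensitive is a mean difference to a few rises? (illustration)**

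The documents give no SD of IOP change, size of rise or frequency. Assumed here: SD 3 to 4 mmHg; k of 86 treated children rise by 10 mmHg; no change on average in anyone else; a simple two-sided z-test at 5% on one comparison.

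- Mean shift = k × 10 / 86: 0.58 mmHg for k = 5, and 0.35 mmHg for k = 3.
- Standard error = SD × √(2/86): 0.46 mmHg (SD 3) or 0.61 mmHg (SD 4).
- Chance of significance = P(Z > 1.96 − shift/SE).

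| | SD 3 | SD 4 |
|---|---|---|
| k = 5 | 0.25 | 0.16 |
| k = 3 | 0.12 | 0.08 |

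These are on the generous side, because the affected children also widen the spread in their arm. Simulation that includes the extra variance gives about 17% and 12% for five children, and about 8 to 9% and 7% for three.

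A wider set of assumptions (SD 2 to 4, rises of 6 to 10 mmHg) gives 5 to 25% when 2 to 5% of the treated arm is affected, and 16 to 61% when 10% is. The mean is therefore weak against rare rises and less weak against common ones.

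**4. Would a count do better as a test?**

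Not by much. Five of 86 against none gives a two-sided Fisher p of 0.059; three against none gives 0.25. Chance also puts controls over a low cut. With normal change, mean zero and a cut of 5 mmHg chosen only for illustration, 86 × P(Z > 5/3) ≈ 4 and 86 × P(Z > 5/4) ≈ 9 children per arm exceed it at one visit. Taking the largest of five visits, with between-visit correlation 0.5 to 0.8, the expected number is roughly 10 to 26 per arm. At 10 mmHg it is about 2 per arm with SD 4 and near zero with SD 3.

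**The case against.** **Individual rises are not lost.** Section 5.2 reports all adverse events individually, raised IOP is a named safety item, and adverse events are recorded at every follow-up visit. A reader might infer that large rises would go unseen under this plan; the documents do not support that, and this part of the objection stands. What remains is narrower. With no definition of raised IOP, six centres must judge when a reading becomes an adverse event. The adverse-event questionnaire in 4.2 is specified only for the intervention group, so elicitation may differ by arm. No by-arm count is planned.

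**A count is not a more powerful test.** This also stands, as step 4 shows. A reader might infer that a count of rises would settle what the mean cannot. Its value is to show the size and distribution of rises in each arm, including those that arise by chance in controls. It should not be read as a significance test.

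**IOP may properly be secondary.** A secondary outcome can be a safety outcome, and adding IOP to 3.5 would also reconcile the text. The efficacy label comes only from the opening of the paragraph in 5.2; the SAP does not otherwise call IOP an efficacy measure. This stands as well: the documents do not require that IOP be struck from the secondary tier, only that it have one tier and be presented as safety.

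**The effect on the trial's inference is small.** The plan states no testing hierarchy among secondary outcomes, so moving IOP reallocates no α. That is correct.

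**Conclusion.** The conflict over IOP's tier is established by the text alone and needs no assumption. It is also established that the specified IOP analysis is a one-eye mean difference, and that raised IOP has neither a definition nor a planned tabulation by arm.

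The size of the insensitivity, about 8 to 25% for three to five large rises, rests wholly on assumed IOP figures and a simplified test. It shows the direction of the problem and does not predict this trial's results. It also does not show that the trial would miss harm, since individual adverse-event reporting remains.

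The point should be addressed because outcome status and safety reporting in children are affected. It does not threaten the axial-length result.

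**What to change.** 1. Give IOP the same status in section 3.5, the abstract's outcome list, the abstract's analysis summary and section 5.2. Report it as a safety outcome rather than under treatment efficacy. If the sponsor wishes to keep it secondary, label it as a secondary safety outcome in all four places.
2. In the safety analysis of 5.2, add a table by arm and visit, for each eye, of the largest per-child rise from baseline and the maximum value, with the number of children in bands that the sponsor defines before the data are examined. The documents contain no cut-offs, and none is proposed here.
3. State how raised IOP is defined for the two safety lists, so that the table and the adverse-event listing can be read together.
4. Keep the mean change by arm as a descriptive summary.

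The cost is a wording change and one extra table from readings already scheduled. The downside is one fewer modelled efficacy outcome. The primary analysis and the sample size stay as they are.
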